4.7 OFF-STUDY CRITERIA

Criteria that can take a participant off-study include:

- Participant requests to be withdrawn from study without further follow-up,
- Completed study follow-up period,
- Death,
- Screen failure

4.7.1 SCREEN FAILURE

Any participant that has signed the consent form (for either screening or study participation) but does not meet the study eligibility criteria, or meets study eligibility criteria but terminates the participation prior to receiving study treatment, will be considered a screen failure. The reason for screen failure should be captured in the database for each participant failing to meet the eligibility criteria.

4.8 STUDY DISCONTINUATION

This study may be temporarily suspended or prematurely terminated if there is sufficient reasonable cause. Written notification, documenting the reason for study suspension or termination, will be provided by the suspending or terminating party to Manufacturer, Sponsor, local IRB or other regulatory agency. If the study is prematurely terminated or suspended, the Investigator will promptly inform the IRB and will provide the reason(s) for the termination or suspension.

Reasons for terminating the study may include the following:

- Incidence or severity of adverse events, in this or other studies, indicates a potential health hazard to participants.

- Interim futility analysis demonstrates that the primary endpoint is unlikely to be met.
- Data that are not sufficiently complete and/or evaluable.
- Investigator(s) do not adhere to the study protocol, or applicable regulatory guidelines in conducting the study.
- Participant enrollment is unsatisfactory.
- Submission of knowingly false information from the study site to Sponsor or regulatory authorities.
- Upon instruction by local or other regulatory, or oversight authority.

Study may resume once concerns about safety, protocol compliance, data quality are addressed and satisfy the Sponsor, IRB and/or FDA.

5. INVESTIGATIONAL PRODUCT

A list of the adverse events and potential risks associated with the investigational or other agents administered in this study can be found in Section 9.4.

5.1 JNJ-40346527

“JNJ-40346527 is a selective inhibitor of CSF-1R tyrosine kinase, with an IC₅₀ of 0.0032 μM. In tissue culture, concentrations of JNJ-40346527 <10 nM are capable of inhibiting monocyte and macrophage responses to CSF-1. JNJ-40346527 is a hydrochloride salt and has a molecular weight of 498.06 and a molecular formula of C₂₇H₃₅N₅O₂•HCl. Refer to investigator brochure for additional details.”^a

5.1.1 ACQUISITION

JNJ-40346527 will be supplied by Manufacturer to the drug distributor Biologics, and prepared by OHSU research pharmacy per manufacturer instructions. Following submission and approval of the required regulatory documents, a supply of JNJ-40346527 may be ordered from Janssen by completing a Drug Request Form.

Allow 4 business days for shipment of drug from receipt of the Drug Request Form. Drug is protocol specific, but not patient specific. There will be no weekend or holiday delivery of drugs.

5.1.1.1 Re-Supply

Drug re-supply request form should be submitted electronically to Biologics no less than 4 business days before the expected delivery date. Deliveries will be made Tuesday through Friday. When assessing need for resupply, the institution should keep in mind that shipments may take 4 business days from time of receipt request. JNJ-40346527 is not patient specific. The investigator or designated study staff is responsible for verifying with research pharmacy the existing stock of study agent to assure optimal use of available drug.

5.1.2 FORMULATION, APPEARANCE, PACKAGING AND LABELING

“JNJ-40346527 drug substance is a white to off-white powder. The active JNJ-40346527 is available as free-base equivalent (eq.) 50 mg and 150 mg hard gelatin capsules. Both capsules are sized 00 opaque capsule. Qualitatively, the hard gelatin capsule contains JNJ-40346527, Microcrystalline Cellulose (filler), Lactose Monohydrate (filler), Hydroxypropyl Methylcellulose (binder), Crospovidone (disintegrant).”

All packages containing investigational product will have the following, or similar, language:
“Caution: New Drug—Limited by Federal law to investigational use.”

5.1.3 PRODUCT STORAGE AND STABILITY

JNJ-40346527 capsules should be stored at room temperature, 15°C to 30°C (59°F to 86°F).

5.1.4 COMPATIBILITY

“JNJ-40346527 is a reversible inhibitor of primarily CYP3A4 and CYP2C8 and to a lesser extent of several other CYP isoforms (ie, CYPs 2B6, 2C9, 2C19, and 2D6) in vitro. JNJ-40346527 increased the plasma exposure of midazolam (by ~65%) in a clinical Phase 1 study, suggesting

a weak inhibition of CYP3A4 at clinically relevant doses.

JNJ-40346527 is an inhibitor of P-gp mediated transport of digoxin in vitro but was not a substrate for P-gp in vitro. Care should be taken if JNJ-40346527 is to be administered with P-gp substrates, especially those with narrow therapeutic index. The clinical impact of co-administration of JNJ-40346527 with known inhibitors and inducers of CYP3A4/5, CYP2C8, or CYP2C19 are not fully understood. An increase or decrease of the systemic exposures of JNJ-40346527 and its active metabolites has to be anticipated”^a

5.1.4.1 Solubility

Very lightly soluble in: 0.1 N HCl, 0.1 N NaOH

Practically insoluble in: H₂O, Citrate/HCl buffer (pH 2-4), Citrate/NaOH buffer (pH 6), Borate/HCl buffer (pH 8), Borate/NaOH buffer (pH 10), simulated intestinal fluid, 20% hydroxypropyl-β-cyclodextrin.

5.1.5 HANDLING

JNJ-40346527 must be dispensed only by the investigator or assigned designee, (e.g., study pharmacist, research nursing staff) to ensure the proper number of capsules are made available to the participants to satisfy dosing requirements for the study. The containers provided to the participant should be labeled with proper instructions for use. The lot numbers, dosing start dates and the number of capsules for each dosage strength must be recorded on the drug accountability pages of record.

5.1.6 PREPARATION

JNJ-40346527 is packaged as hard gelatin capsules. No additional preparation is required.

5.1.7 ADMINISTRATION

JNJ-40346527 will be supplied by Janssen Research & Development, LLC. or its designee in the form of 50 mg and 150 mg hard gelatin capsules as individual participant supply packaged in bottles. JNJ-40346527 is to be taken orally, twice daily. JNJ-40346527 must be taken as follows:

- Participants should be instructed to take the JNJ-40346527 capsules with a large glass of water (~250ml) at the same time each day.
- Participants should be instructed to swallow the JNJ-40346527 capsules whole and not to chew, crush or open them.
- JNJ-40346527 can be taken without regard to meals, preferably right after breakfast and dinner. Anti-acids may affect absorption, suggest adding to use them only 2 hours or more before or after any doses of study drug.
- Regardless, dietary habits around the time of dosing should be as consistent as possible throughout the study, and in particular during those periods when samples are being taken for PK analysis.
- If vomiting occurs during the course of treatment, no re-dosing of the participant is allowed before the next scheduled dose.
- Any doses that are missed (not taken within 6 hours of the intended time) should be skipped and should not be replaced or made up on a subsequent day.

- Participants must avoid consumption of grapefruit, grapefruit hybrids, pummelos, star-fruit, Seville oranges or products containing the juice of each during the entire study and preferably 7 days before the first dose of study medication, due to potential CYP3A4 interaction with the study medication. Orange juice is allowed.
- Due to potential interactions with JNJ-40346527, no herbal or dietary supplements are permitted, including St. John's Wort without provider consultation.
- Multivitamins are allowed.
- Refer to Appendix C for tables of prohibited medications and medications to be used with caution in association with administration of JNJ-40346527.
- If a subject is taking frequent antacids, e.g. always take JNJ-40346527 with food, ie, within approximately 30 minutes after breakfast in the morning and within approximately 30 minutes after their evening meal.

5.1.8 SPECIAL CONSIDERATIONS FOR ADMINISTRATION

5.1.8.1 Participant self-administration

JNJ-40346527 may be self-administered by participant. Specific instructions for at-home administration of JNJ-40346527 must be given to participant by physician or other designated healthcare provider.

5.1.8.2 Participant Medical Diary

Participants are required to keep a medical diary to record ingestion of study agent (e.g., frequency, volume of water per ingestion, as well as duration between meals).

5.1.9 ACCOUNTABILITY

The Investigator, or a responsible party designated by the Investigator, must maintain a careful record of the inventory and disposition of the study agent. (See the [NCI Investigator's Handbook for Procedures for Drug Accountability and Storage](#)).

Responsibility for drug accountability at the study site rests with the Investigator; however, the Investigator may assign some of the drug accountability duties to an appropriate pharmacist or designee. Inventory and accountability records must be maintained and readily available for inspection by the study monitor and are open to inspection at any time by any applicable regulatory authorities or other oversight bodies.

The Investigator or designee will collect and retain all used, unused, and partially used containers of study medication until full accounting has been completed. The Investigator or designee must maintain records that document:

- Investigational product delivery to the study site.
- The inventory at the site.
- Use by each participant including pill/unit counts from each supply dispensed.
- Return of investigational product to the Investigator or designee.
- Destruction or return of investigational product for final disposal.

These records should include dates, quantities, batch/serial numbers (if available), and the unique code numbers (if available) assigned to the investigational product and study participants.

The investigational product must be used only in accordance with the protocol. The Investigator will also maintain records adequately documenting that the participants were provided the correct study medication specified.

Completed accountability records will be archived by the site. At the completion of the study, the Investigator or designee will oversee shipment of any remaining study drug back to the Manufacturer for destruction according to institutional standard operating procedures. If local procedures mandate site destruction of investigational supply, prior written approval must be obtained from Manufacturer.

5.1.10 DESTRUCTION AND RETURN

At the end of the study, or earlier upon approval from study management, unused supplies of JNJ-40346527 should be destroyed according to institutional policies. Drug supplies will be counted and reconciled in full at the site with all monitoring procedures complete before destruction. Destruction will be documented in the Drug Accountability Record Form.

6. TREATMENT PLAN

6.1 DOSAGE AND ADMINISTRATION

JNJ-40346527 will be administered at a fixed dose of 150 mg PO twice daily in continuous 28 day cycles (defined as a single treatment cycle). Treatment will be administered on an out-patient basis. Reported adverse events and potential risks are described in [Section 9](#). Appropriate dose modifications are described in Section 6.2. No investigational or commercial agents or therapies other than those described below may be administered with the intent to treat the participant's malignancy.

Regimen Description				
Agent	Premedication; Precautions	Dose	Route	Cycle Length
JNJ-40346527		150 mg, b.i.d	PO	28 Days

6.2 DOSING DELAYS AND MODIFICATIONS

6.2.1 DEFINITION OF DOSE-LIMITING TOXICITY (DLT)

A DLT is defined as an adverse event or abnormal laboratory value assessed as unrelated to disease, disease progression, inter-current illness, or concomitant medications. A DLT requires a definite, probable or possible adverse experience to be related to the investigational product. Toxicities will be assessed using the National Cancer Institute Common Terminology Criteria for Adverse Events (NCI [CTCAE v5](#)).

Safety will be assessed by evaluating the incidence of DLTs that exceeds the expected toxicities associated with JNJ-40346527. That is, DLTs are defined as any \geq Grade 3 treatment related toxicity according to CTCAE v5.0. The following expected adverse events are excluded:

- Grade 3 and 4 prolonged hematologic toxicities
- Grade 3 AST levels (i.e., >5 to $20 \times$ ULN)
- Grade 3 Creatinine kinase (CK) levels (i.e., >3.0 baseline; >3.0 - $6.0 \times$ ULN)

A DLT will also be defined as:

- (1) An ANC that fails to recover to >0.5 Gi/L within 42 days from the start of therapy in the absence of active leukemia or myelodysplasia; and,
- (2) A platelet count that fails to recover to >20 Gi/L within 42 days from the start of therapy in the absence of active leukemia or myelodysplasia or that is associated with clinically significant bleeding that requires transfusion of red cells or platelets.

6.2.1.1 Duration of DLT assessment

The DLT evaluation period will begin with the first dose of JNJ-40346527 and be continuously assessed throughout the study.

6.2.2 DOSE DELAYS

Treatment may be delayed for up to 28 days from the end of a previous 28-day cycle for SAEs described in Table 4. In case of a treatment delay subsequent study assessment days will be adjusted accordingly.

6.2.3 DOSE ESCALATION

No dose escalation is allowed. JNJ-40342527 will be administered at a fixed dose of 150mg twice daily.

6.2.4 DOSE DE-ESCALATION

Dose reductions are allowable per PI discretion. If treatment-related toxicities are observed that based on the investigator's best clinical judgement require a dose reduction, the dose of JNJ-40346527 can be reduced to 100 mg PO BID. The dose of JNJ-40346527 can be reduced only once. In case of another episode of treatment-related toxicity which based on the investigator's best clinical judgement requires a dose reduction, the study treatment with JNJ-40346527 needs to be discontinued.

6.2.5 GENERAL DOSE DELAY GUIDELINES

Dose delays will be made as indicated in **Table 4**. The descriptions and grading scales found in the revised [CTCAE v5](#) will be utilized for dose delays.

Table 4. Dose delay guidelines and management of next dose for JNJ-40346527

Non-hematologic	
≤Grade 1	No dose modification.
Grade 2	No dose modification.
Grades 3-4 and clinically significant*	Dose modification per PI discretion.
Hematologic	
All grades	Dose modification per PI discretion.

*For non-hematologic grade 3 and 4 AEs, JNJ-40346527 will be held until toxicity resolves to grade <2. Once grade <2, JNJ-40346527 will be restarted at 50 mg BID, then increased to 100 mg BID, and finally to 150 mg BID if subject was felt to be deriving clinical benefit and would like to continue on study. This dose escalation regimen will be reviewed by the treating physician and medical monitor.

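### After the same severe drug-related event, section 6.2.4 and the Table 4 footnote lead to different doses, and nothing says which governs

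*Combined protocol and SAP*

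**What the plan says.** Section 6.1 sets a fixed dose of 150 mg twice daily and refers to section 6.2 for modifications. Two parts of section 6.2 deal with lowering the dose.

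- **Section 6.2.4 (dose de-escalation).** For treatment-related toxicity that the investigator judges to require a reduction, "the dose of JNJ-40346527 can be reduced to 100 mg PO BID". It adds: "The dose of JNJ-40346527 can be reduced only once". If another episode requires a reduction, "the study treatment with JNJ-40346527 needs to be discontinued". It sets no limit by grade or by type of event, and it does not mention a return to 150 mg BID.
- **Section 6.2.5, Table 4 and its footnote.** For non-hematologic grade 1 and grade 2 events the table says "No dose modification". For clinically significant non-hematologic grade 3-4 events the row says "Dose modification per PI discretion" and carries an asterisk. The footnote says that for non-hematologic grade 3 and 4 events the drug "will be held until toxicity resolves to grade <2". On what follows the hold, it says: "JNJ-40346527 will be restarted at 50 mg BID, then increased to 100 mg BID, and finally to 150 mg BID". A condition is attached to that sentence: the participant must be thought to benefit and must want to stay in the trial. The treating physician and the medical monitor review this regimen. The footnote says nothing about repeat episodes.

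Neither section refers to the other. The schedule of events (section 7.10), like section 6.1, points to section 6.2 as a whole.

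**The concern.** Some events meet both triggers: those that are treatment-related, non-hematologic, grade 3-4 (and clinically significant, if the row limits the footnote) and judged to need a lower dose. For these, the two texts give different first doses and different later courses. Only the footnote provides for a return to the full dose. Only section 6.2.4 requires discontinuation at a second episode.

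Participant safety and uniform conduct are at stake. Section 4.3.1 plans accrual at the coordinating center and two participating sites. These could give different doses after the same severe toxicity, or differ on whether a recurrence ends treatment, and each could cite the protocol.

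**Working it through.** No statistical figure is involved, so the check is a side-by-side reading plus daily totals.

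**1. Do the triggers overlap?**

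| | Section 6.2.4 | Table 4 footnote |
|---|---|---|
| Relatedness | Treatment-related | Not limited |
| Event type | Not limited | Non-hematologic |
| Grade | Not limited | 3 and 4 (row adds clinical significance) |
| Judgement | Investigator judges a reduction necessary | Row leaves modification to the PI; footnote is directive |
| Hold first | Not mentioned | Yes, until grade <2 |
| First lower dose | 100 mg BID | 50 mg BID |
| Return to 150 mg BID | Not mentioned | Yes, conditional |
| Repeat episode needing reduction | Discontinue | Not mentioned |

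An event that satisfies both columns is possible, and it is foreseeable. Section 6.2.1 lists grade 3 AST and CK elevations among expected events. Section 9.4.1 reports grade 3 events in 7 (33%) participants, with non-hematologic terms among them. Those figures are not split by relatedness or by need for a reduction, so they show only that the situation is realistic.

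**2. How far apart are the doses?** Daily total = 2 × the single dose.

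- Planned: 2 × 150 = 300 mg/day.
- Section 6.2.4: 2 × 100 = 200 mg/day; 200/300 = 66.7% of planned.
- Footnote restart: 2 × 50 = 100 mg/day; 100/300 = 33.3%.
- Footnote second step: 2 × 100 = 200 mg/day; 66.7%.
- Footnote last step: 2 × 150 = 300 mg/day; 100%.

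At restart, section 6.2.4 gives 200/100 = 2.0 times the footnote dose. At the second step the two are equal. At the last step the footnote gives 300/200 = 1.5 times the section 6.2.4 dose. Sustained exposure cannot be compared, because the footnote gives no step duration and section 1.3.3.1 puts steady state at about 21 days of dosing.

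**3. Does any reading settle it?** Two are possible.

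- *Section 6.2.4 covers reduction without a hold; the footnote covers restart after a hold.* The protocol does not draw this line.
- *The footnote is the specific rule and displaces section 6.2.4 for its events.* This is not stated either.

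Because Table 4 allows no modification for non-hematologic grades 1 and 2, either reading would leave section 6.2.4 mainly for hematologic events, a limit that its own wording does not contain. Under both readings it stays open whether a 50 mg BID restart counts as the single reduction and whether the discontinuation rule applies afterwards. The benefit condition in the footnote is also ambiguous: it may govern the restart itself or only the increases.

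**4. Two smaller wording points nearby.** Section 6.2.2 caps delays at 28 days for SAEs in Table 4, although that table grades AEs. Section 6.2.3 rules out dose escalation, while the footnote describes its own steps as an escalation regimen; section 6.2.3 may be meant only to bar doses above 150 mg BID.

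**The case against.** The best defense is that the texts can be read together. Section 6.2.4 is permissive, since it allows 100 mg BID at the PI's discretion and never mandates it. The footnote is directive for a narrower class. The headings support a division: one section concerns de-escalation, while the other, with its table, concerns delays and management of the next dose. On that view section 6.2.4 still does real work, because Table 4 leaves hematologic events of every grade to discretion without naming a dose. The clinical-significance qualifier on the table row may narrow the overlap further. Some variation between sites is also the intended result of PI discretion. Oversight exists as well: medical monitor review of the footnote regimen, the pause in section 9.7 for unmanageable or unexpected attributable grade 4 toxicity, and DSMC review under section 11.1.

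Much of this is fair. The permissive wording means that these are not two mandatory doses for one event, the headings are evidence for one reconciling reading, and the qualifier may shrink the class somewhat. But none of it is stated as a rule. Discretion over whether to modify the dose does not say which text applies once the decision is made, and the oversight bodies are given no rule to apply. The defense also leaves unanswered whether a footnote restart consumes the single reduction and what follows at a second episode.

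**Conclusion.** The concern holds: the plan is wrong as written on this point. For treatment-related, non-hematologic grade 3-4 events judged to need a lower dose, it contains two stated courses and no order between them. The first dose after the event differs twofold (200 versus 100 mg/day). If the footnote steps are completed, the difference reverses to a ratio of 1.5 (200 versus 300 mg/day). Whether a second episode requires discontinuation is undetermined.

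This rests on the wording alone and on taking 100 mg BID as the dose given when the section 6.2.4 permission is used. The number of participants affected cannot be derived from the documents; planned enrollment is at most 28. Power and sample size do not change.

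**What to change.** The sponsor and the medical monitor should reconcile section 6.2.4, the Table 4 row and the Table 4 footnote into one rule. It should state:

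- which events it covers, including whether clinical significance is required;
- whether a restart under the footnote counts as the single permitted reduction;
- how a repeat episode after such a restart is handled;
- whether the benefit condition applies to the restart or only to the increases.

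Sections 6.2.2 and 6.2.3 should then be aligned with that rule. Which dose or rule to adopt is for the sponsor and the medical monitor to decide. The cost is protocol amendment wording, with no statistical cost.

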6.3 TREATMENT PERIOD AND MAINTENANCE

Participants will receive JNJ-40346527 at 150 mg PO twice daily in continuous 28-day cycles. Initial response will be assessed by bone marrow biopsy after cycles 1-3 and then every 3 months thereafter. Further study assessments will be performed as outlined in the Section 7.10, Schedule of Events .

Treatment with JNJ-40346527 will continue until disease progression or stopping rules are triggered as a result of either excess toxicity or lack of efficacy (refer to Section 10.2.4).

Disease progression will be defined as any patient with response \geq PR who then loses PR based upon the original pre-treatment marrow sample (PR defined as \geq 50% decrease in marrow blasts to 5-25% of marrow). For example, a patient with 30% blasts on pre-treatment

marrow who achieved CR with 4% blasts and then was found to have 6% blasts with continued hematologic recovery on subsequent marrow (PR) would remain on trial until subsequent marrow blasts were >15%, or with loss of hematologic response. Patients with stable disease who continue to receive clinical benefit per PI review may remain on study drug.

If a participant achieves a complete remission (CR) and is deemed a candidate for allogeneic stem-cell transplant, JNJ-40346527 should be discontinued 7 days before initiation of the conditioning regimen. Treatment with JNJ-40346527 may be resumed 30-100 days after the transplant if patients has a relapse of their disease, no active GVHD, and after review by the PI.

